7.2 Analysis of Primary/Secondary Endpoints of Immunogenicity

The immunogenicity analysis will be performed using the first PP Analysis Set (PP1) and the second PP Analysis Set (PP2). No missing data will be imputed. Titers/ELISA Units reported below the lower limit of quantification (LLOQ) will be set to half that limit (ie, if LLOQ=10, then 10/2 = 5) for use in computations.

7.2.1 Nab Titers for SARS-CoV-2

As the primary objectives of charactering Nab response to ancestral strain Novavax vaccine administered as a second (or subsequent) booster after licensed mRNA vaccines and a first ancestral strain Novavax vaccine booster, the derived/calculated endpoints of Nab response for **the group receiving ancestral strain Novavax vaccine** will include:

- Nab GMT is calculated as the antilog of the mean of the log-transformed Nab titers. Nab GMT will be summarized by visit day (Days 1 and 29) along with the corresponding 2-sided 95% CIs, by exponentiating the corresponding log-transformed means and their 95% CIs.

- GMFR_{Post/Pre} is calculated as the within-group ratio of post-vaccination Nab GMT at Day 29 to pre-vaccination Nab GMT at the baseline (Day 1).
 - GMFR_{Post/Pre} will be calculated using this formula:

$$GMFR_{Post/Pre} = 10^{\left(\frac{\sum_{i=1}^n \log_{10} \frac{v_{ij}}{v_{ik}}}{n} \right)} = 10^{\frac{\{\sum_{i=1}^n (\log_{10} v_{ij} - \log_{10} v_{ik})\}}{n}}$$

where, for n participants, v_{ij} and v_{ik} are observed immunogenicity titers for subject i at time points j (post-vaccination at Day 29) and k (pre-vaccination at Day 0).

- Below sample SAS code will be conducted using paired t distribution to estimate GMFR_{Post/Pre} and corresponding 95% CIs.

```
proc means data=Nab_D1andD29_nonmissing n mean std t prt clm;
  var diff_aval;
  output out=paired N=n MEAN=mean STDEERR=stderr STD=stddev
  LCLM=lclm UCLM=uclm prt=prt;
run;
```

- GMR_{312/307} defined as the ratio of Nab Geometric Mean Titer (GMT) **28 days after a second (or subsequent) booster dose** of NVX-CoV2373 in Study **2019nCoV-312** versus **28 days after a first booster dose** of NVX-CoV2373 in Study **2019nCoV-307** among the same participants with the corresponding 95% CIs will be conducted using paired t distribution. Non-inferiority will be demonstrated if GMR_{312/307} of Nab titers is higher than 0.67 and superiority will be demonstrated if GMR_{312/307} of Nab titers is higher than 1.0 after non-inferiority is successfully demonstrated.

- GMR_{312/307} will be calculated using this formula:

$$GMR_{312/307} = 10^{\left(\frac{\sum_{i=1}^n \log_{10} \frac{v_{ij}}{v_{ik}}}{n} \right)} = 10^{\frac{\{\sum_{i=1}^n (\log_{10} v_{ij} - \log_{10} v_{ik})\}}{n}}$$

where, for n subjects, v_{ij} and v_{ik} are observed immunogenicity titers for subject i at time points j (28 days after a second (or subsequent) booster dose of NVX-CoV2373 in Study 2019nCoV-312) and k (28 days after a first booster dose of NVX-CoV2373 in Study 2019nCoV-307).

As the 1st secondary objectives of characterizing Nab response to ancestral strain Novavax vaccine administered as a second (or subsequent) booster after licensed mRNA vaccines and a first ancestral strain Novavax vaccine booster, the derived/calculated endpoints of Nab response for **the group receiving ancestral strain Novavax vaccine** will include:

- SCR is defined as proportion of participants who achieve seroconversion \geq 4-fold increase from baseline in Nab titers at Day 29 if the baseline value is equal to or above LLOQ or at least 4-fold fold rise from LLOQ if the baseline value is lower than LLOQ.

- SCR in Nab GMEUs with corresponding two-sided exact binomial 95% CIs will be calculated using the Clopper-Pearson method with the following sample SAS code:

```
proc freq data=Nab noint;
  tables seroconvind / binomial(exact) alpha=.05;
  output out=out1 binomial;
run;
```

- Two-sided 95% CIs of the difference in SCRs in Nab titers **28 days after a second (or subsequent) booster dose** of NVX-CoV2373 in Study **2019nCoV-312** relative to time of Day 1 dose in Study **2019nCoV-307** versus **28 days after a first booster dose** of NVX-CoV2373 in Study **2019nCoV-307** relative to time of Day 1 dose in Study **2019nCoV-307** among the same participants will be based on the method of confidence interval for the difference in two correlated proportions by Tango (SAP Section [11.6](#)). Non-inferiority will be demonstrated if the LB of the 95% exact CIs for the difference of SCRs ($SCR_{312} - SCR_{307}$) in Nab titers is higher than -10%.

As the 3rd secondary objectives of characterizing the cross-reaction of neutralizing and IgG antibodies induced by the ancestral strain Novavax vaccine to more recent SARS-CoV-2 variants and any other variants for which appropriate assays are available, the derived/calculated endpoints of Nab response for **the group receiving updated Novavax COVID-19 Vaccine based on recent variant(s)** will include Nab GMTs at Days 1 and 29, $GMFR_{Post/Pre}$ (Day 29 vs. Day 1), $GMR_{312/307}$, SCRs (Day 29 vs. Day 1), and difference in SCRs ($SCR_{312} - SCR_{307}$) in Nab titers to be calculated using the same calculations and comparison periods as noted above for **the group receiving ancestral strain Novavax vaccine**.

Above parameters based on the Pseudovirus-based Nab response per Wuhan strain from Study 2019nCoV-307 tested by Monogram will be presented together with the summary of Study 2019nCoV-312 to evaluate the primary endpoints of Nab response.

Since the Pseudovirus-based Nab response (Wuhan) at 4 different visits including the date of 1st booster dose (Day 1 in 2019nCoV-307), 28 days after 1st booster dose (Day 29 in 2019nCoV-307), date of 2nd booster dose (Day 1 in 2019nCoV-312) and 28 days after 2nd booster dose (Day 29 in 2019nCoV-312) were tested using the similar Pseudovirus Neutralization Assay by two different labs of Monogram and NVX CI, below conversions will be applied to the individual value in the unit of ID50 to the value in the standard unit of IU/mL.

2019nCoV-307 (Monogram): $ID50 * 0.1458 = IU/mL$

2019nCoV-312 (NVX CI): $ID50 * 0.214 = IU/mL$ Pseudovirus-based Nab response (Omicron BA.5) of Study 2019nCoV-312 will be presented including GMT, $GMFR_{Post/Pre}$ and SCR.

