2 OBJECTIVES AND ENDPOINTS

An overview of all study objectives and endpoints is provided in [Table 3](#).

Table 3: Study 2019nCoV-312 Objectives and Endpoints

	Objectives	Endpoints
Primary	To characterize the Nab responses (geometric mean titers, GMTs) to ancestral strain Novavax vaccine administered as a second (or subsequent) booster after licensed mRNA vaccines and a first ancestral strain Novavax vaccine booster	
• Nab GMTs to the ancestral strain SARS-CoV-2 at Day 29. Non-inferiority will be demonstrated if the lower-bound (LB) of the 95% CIs for the ratio of Nab GMT at Day 29 between the two booster periods is > 0.67.• If non-inferiority is demonstrated, results will be tested for superiority, defined as the LB of 95% CIs for the ratio of Nab GMT at Day 29 > 1.0.
Secondary	To further characterize the Nab responses (seroconversion rate, SCR) to ancestral strain Novavax vaccine administered as a second (or subsequent) booster after licensed mRNA vaccines and a first ancestral strain Novavax vaccine booster.	Proportion of participants who achieve seroconversion (≥ 4 -fold increase from baseline) in neutralization antibody titers to the SARS-CoV-2 at Day 29 compared with results of the same measurements in participants who received their first ancestral strain Novavax vaccine booster after mRNA vaccination in Study 2019nCoV-307. Non-inferiority will be demonstrated if the LB of the 95% exact CIs for the difference of SCRs in Nab titers is higher than -10%

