	To demonstrate the noninferior immunogenicity of Novavax vaccine as a second (or subsequent) booster vs as a first booster of ancestral strain Novavax vaccine boost following mRNA vaccines.	
• IgG geometric mean enzyme-linked immunoassay (ELISA) unit concentrations (GMEU/mL) to the SARS-CoV-2 ancestral strain spike protein at Day 29; Non-inferiority will be demonstrated if the lower-bound (LB) of the 95% CIs for the ratio of IgG GMEU at Day 29 between the two booster periods is > 0.67.• If non-inferiority is demonstrated, results will be tested for superiority, defined as a lower 95% confidence interval of GMEU ratio > 1.0.• Proportion of participants who achieve seroconversion (≥ 4-fold increase from baseline) in IgG concentrations to the SARS-CoV-2 ancestral strain spike protein at Day 29 compared with results of the same measurements in participants who received their first ancestral strain Novavax vaccine booster after mRNA vaccination in Study 2019nCoV-307. Non-inferiority will be demonstrated if the LB of the 95% exact CIs for the difference of SCRs in IgG ELISA unit is higher than -10%.
	To characterize the cross-reaction of neutralizing and IgG antibodies induced by the ancestral strain Novavax vaccine to more recent SARS-CoV-2 variants and any other variants for which appropriate assays are available.	Post-booster neutralizing GMTs and IgG GMEUs compared with post-first booster results from Study 307.

Table 3: Study 2019nCoV-312 Objectives and Endpoints

	Objectives	Endpoints
Secondary (cont.)	To further characterize antibody responses in a human angiotensin-converting enzyme 2 (hACE2) receptor binding inhibition assay to the SARS-CoV-2 ancestral strain spike protein using the same calculations and comparison group as noted above for neutralizing and IgG antibodies.	Seroresponse data from Study 307 participants enrolled to the second treatment group of this study to receive an updated Novavax vaccine based on recent variant will be assayed using the same assays as described above. hACE2 antibodies post-updated booster will be compared to those post-ancestral strain boosters and will be analyzed in the same manner specifically to assess reactivity with the ancestral strain virus/spike protein and with recent variant virus/spike protein.

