7 ANALYSES ADDRESSING PROTOCOL OBJECTIVES

7.1 Statistical Hypothesis

FoFor To evaluate the Nab responses to ancestral strain Novavax vaccine administered as a second (or subsequent) booster after licensed mRNA vaccines and a first ancestral strain Novavax vaccine booster, two statistical hypotheses will be evaluated in the group receiving **ancestral strain NVX-CoV2373.**

- Non-inferiority of a second (or subsequent) booster dose of NVX-CoV2373, as measured by the lower-bound (LB) of the 95% confidence interval (CI) for $GMR_{312/307}$ defined as the ratio of Nab Geometric Mean Titer (GMT) **28 days after a second (or subsequent) booster dose** of NVX-CoV2373 in Study **2019nCoV-312** versus **28 days after a first booster dose** of NVX-CoV2373 in Study **2019nCoV-307** among the same participants being > 0.67 . This is expressed statistically as:

$$\begin{aligned} H_0: GMR_{312/307} &\leq 0.67 \\ H_1: GMR_{312/307} &> 0.67 \end{aligned}$$

[figure not shown]
- Non-inferiority of a second (or subsequent) booster dose of NVX-CoV2373, as measured by the lower-bound (LB) of the 95% exact CI for the difference of proportion of participants with seroconversion (SCR) in Nab titers **28 days after a second (or subsequent) booster dose** of NVX-CoV2373 in Study **2019nCoV-312** relative to time of Day 1 dose in Study **2019nCoV-307** versus **28 days after a first booster dose** of NVX-CoV2373 in Study **2019nCoV-307** relative to time of Day 1 dose in Study **2019nCoV-307** among the same participants being $> -10\%$. This is expressed statistically as:

$$\begin{aligned} H_0: SCR_{312} - SCR_{307} &\leq -10\% \\ H_1: SCR_{312} - SCR_{307} &> -10\% \end{aligned}$$

Successful demonstration of non-inferiority of the booster dose requires lower-bound (LB) of the 95% confidence interval (CI) for $GMR_{312/307}$ defined as the ratio of Nab Geometric Mean Titer (GMT) **28 days after a second (or subsequent) booster dose** of NVX-CoV2373 in Study **2019nCoV-312** versus **28 days after a first booster dose** of NVX-CoV2373 in Study **2019nCoV-307** among the same participants being > 0.67 to meet the primary endpoint ([Figure 2](#)). If non-inferiority is demonstrated, successful demonstration of superiority being $GMR_{312/307} > 1.0$ will meet the primary endpoint.

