7.2.2 ELISA (IgG) ELISA Units for SARS-CoV-2

As the 2nd secondary objectives of demonstrating the noninferior immunogenicity of Novavax vaccine as a second (or subsequent) booster vs as a first booster of ancestral strain Novavax vaccine boost following mRNA vaccines, the derived/calculated endpoints of IgG response for **the group receiving ancestral strain Novavax vaccine** will include:

- IgG GMEU is calculated as the antilog of the mean of the log-transformed IgG GMEU. IgG GMEU will be summarized by visit day (Days 1 and 29) along with the corresponding 2-sided 95% CIs, by exponentiating the corresponding log-transformed means and their 95% CIs.
- GMFR_{Post/Pre} is calculated as the within-group ratio of post-vaccination IgG GMEU at Day 29 to pre-vaccination IgG GMEU at the baseline (Day 1). Similar sample SAS code as Nab will be applied to estimate IgG GMFR_{Post/Pre} and corresponding 95% CIs.
- GMR_{312/307} of IgG GMEU **28 days after a second (or subsequent) booster dose** of NVX-CoV2373 in Study **2019nCoV-312** versus **28 days after a first booster dose** of NVX-CoV2373 in Study **2019nCoV-307** among the same participants with corresponding 95% CIs will be conducted using paired t distribution. Non-inferiority will be demonstrated if GMR_{312/307} of IgG GMEU is higher than 0.67 and superiority will be demonstrated if GMR_{312/307} of IgG GMEU is higher than 1.0 after non-inferiority is successfully demonstrated.
- SCR is defined as proportion of participants who achieve seroconversion \geq 4-fold increase from baseline in IgG GMEUs at Day 29 if the baseline value is equal to or above LLOQ or at least 4-fold fold rise from LLOQ if the baseline value is lower than LLOQ. SCR in IgG GMEUs with corresponding two-sided exact binomial 95% CIs will be calculated using the Clopper-Pearson method.

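### The SAP's detailed analysis sections state the GMR success rule without the 95% CI lower bound that SAP Table 3 and the protocol require

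*SAP*

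**What the plan says.** **Rules without a bound.** SAP 7.2.1 (Nab) reads "Non-inferiority will be demonstrated if GMR_{312/307} of Nab titers is higher than 0.67 and superiority will be demonstrated if GMR_{312/307} of Nab titers" exceeds 1.0, once non-inferiority is shown. The same bullet defines GMR312/307 by formula as 10 raised to the mean of the observed log10 ratios, so the quantity compared with 0.67 is the estimate. SAP 7.2.2 repeats the pattern for IgG: "Non-inferiority will be demonstrated if GMR_{312/307} of IgG GMEU is higher than 0.67", with superiority above 1.0. In SAP 7.1 the superiority sentence begins "If non-inferiority is demonstrated, successful demonstration of superiority being" and ends with GMR312/307 > 1.0, again with no bound.

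**Rules with the bound.** For primary non-inferiority, SAP 7.1 says "Successful demonstration of non-inferiority of the booster dose requires lower-bound (LB) of the 95% confidence interval (CI) for" the ratio to exceed 0.67. SAP Table 3 says for Nab "Non-inferiority will be demonstrated if the lower-bound (LB) of the 95% CIs for the ratio of Nab GMT at Day 29" exceeds 0.67, and for IgG "Non-inferiority will be demonstrated if the lower-bound (LB) of the 95% CIs for the ratio of IgG GMEU at Day 29" exceeds 0.67. It defines superiority for both assays by the lower limit exceeding 1.0. Protocol 9.3.2, the protocol synopsis and protocol Table 2 agree with SAP Table 3.

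**Display.** SAP section 11, Table 5, reports GMR312/307 and its CI to one decimal.

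**The concern.** An estimate above 0.67 and a lower confidence limit above 0.67 are different criteria, and the SAP contains both for the same endpoint. Section 7.2 holds the formulas and sample code, so it is the natural source for programming and for the study report.

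Two features make the omission harder to dismiss:

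- The seroconversion rule in the same section 7.2.1 does name the bound ("Non-inferiority will be demonstrated if the LB of the 95% exact CIs for the difference of SCRs"), so the ratio sentence can be read as deliberately different.
- SAP 7.1 settles only one of the four ratio verdicts. It announces that "two statistical hypotheses will be evaluated in the group receiving" ancestral-strain vaccine, and both hypotheses are Nab non-inferiority (ratio and seroconversion). For Nab superiority and for both IgG verdicts, Table 3 is the only place in the SAP that holds the lower-bound rule.

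At stake is whether a verdict, including the primary one, depends on which section was programmed.

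**Working it through.** **Inputs.** Paired t on the log10 ratio (SAP 7.2.1); margin 0.67 (SAP 7.1); SD 0.61 log10 and at least 90% power (SAP 1.2); two-sided 95% CI, hence one-sided 0.025; n = 129 (SAP Table 2, true ratio 1.0). The ancestral-strain group is planned at 100 to 150. SDs of 0.50, 0.40 and 0.30 are my assumptions, used because the SAP describes 0.61 as an 80% confidence upper bound.

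**1. Which rule produced the sample sizes?** I computed the smallest n with 90% power, using the noncentral t for the lower-bound rule. For the point-estimate rule, n = (SD × 1.2816 / δ)², where δ = log10(true ratio) − log10(margin).

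| True ratio | SAP Table 2 | Lower bound, margin 2/3 | Lower bound, margin 0.67 | Point estimate, margin 2/3 |
|---|---|---|---|---|
| 1.0 | 129 | 129 | 132 | 20 |
| 1.1 | 85 | 85 | 87 | 13 |
| 1.2 | 62 | 62 | 63 | 10 |
| 1.3 | 49 | 49 | 50 | 8 |
| 1.4 | 40 | 40 | 41 | 6 |
| 1.5 | 34 | 34 | 34 | 5 |

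The lower-bound rule matches all six rows at margin 2/3 and comes within three participants at the stated 0.67. For a point-estimate rule at margin 0.67 and true ratio 1.0, (0.61 × 1.2816 / 0.1739)² = 20.2, so 21. Table 2 was built on the lower-bound rule.

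**2. Where do the two rules disagree?** The lower bound exceeds m only if the observed ratio exceeds m × 10^h, with h = t(0.975, n−1) × SD / √n. For n = 129 and SD 0.61, h = 1.979 × 0.61 / 11.358 = 0.1063 and 10^h = 1.277. The thresholds are 0.67 × 1.277 = 0.856 for non-inferiority and 1.277 for superiority. Observed ratios that pass 7.2.1 but fail Table 3:

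| n | SD | Non-inferiority | Superiority |
|---|---|---|---|
| 100 | 0.61 | 0.67 to 0.885 | 1.0 to 1.321 |
| 129 | 0.61 | 0.67 to 0.856 | 1.0 to 1.277 |
| 150 | 0.61 | 0.67 to 0.840 | 1.0 to 1.254 |
| 129 | 0.50 | 0.67 to 0.819 | 1.0 to 1.222 |
| 129 | 0.40 | 0.67 to 0.787 | 1.0 to 1.174 |
| 129 | 0.30 | 0.67 to 0.756 | 1.0 to 1.128 |

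**3. Error rates under a literal reading.** P(observed ratio > 0.67) = 1 − Φ[(log10 0.67 − log10 true ratio) × √n / SD].

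- True ratio 0.67: 50% at any SD, against 2.5% under the lower-bound rule. A simulation of 200,000 trials gave 50.2% and 2.5%.
- True ratio 0.60, n = 129, SD 0.61: 0.0479 × 11.358 / 0.61 = 0.892, so 18.6%, against 0.2% under the lower-bound rule. At SDs of 0.50, 0.40 and 0.30 the literal rule gives 13.8%, 8.7% and 3.5%.
- Superiority at a true ratio of 1.0: 50% against 2.5%.

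**4. Rounding.** One decimal hides the verdict only when the lower bound prints as 0.7 (0.65 to 0.75) or as 1.0 (0.95 to 1.05). In 400,000 simulated trials at a true ratio of 1.0, n = 129 and SD 0.61, the lower bound fell between 0.65 and 0.75 in 29.5%.

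**The case against.** The best reply is that this is a drafting slip which the documents already resolve. SAP Table 3 gives the lower-bound rule for all four verdicts, the protocol agrees, and SAP 1.3 says the analyses follow the protocol. In 7.2.1 and 7.2.2 the sentence just before the rule asks for GMR312/307 with its 95% CIs by paired t, and nowhere is a point estimate said to suffice. The 7.1 superiority phrase can be read as the hypothesis to be demonstrated, since 7.1 writes its non-inferiority hypotheses in the same notation. The SAP is loosely worded in other places, so the contrast with the seroconversion rule is weak evidence of intent. The 50% figure holds for any point-estimate rule at its own threshold.

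Most of this stands as a statement about intent: the lower-bound rule was meant, and no choice of test, margin or sample size is in dispute. It does not remove the conflict. Two sections state a decision rule that gives a different verdict if followed, one of them for the primary endpoint, and SAP 7.1 does not correct it for superiority or IgG. The rounding point is fairly called secondary, because nothing in the SAP says verdicts are judged on rounded values.

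**Conclusion.** The concern holds: the SAP contradicts itself on the success rule for GMR312/307. The disagreement ranges above (0.67 to 0.856 and 1.0 to 1.277 at n = 129) rest on the planning SD of 0.61. They narrow with a smaller SD but remain at 0.30. The Nab SD is used throughout; the documents give none for IgG, so the ranges for IgG are unknown, though the 50% at the threshold would apply there too. With the lower-bound rule in every section, one-sided error is 2.5% for both verdicts. Power for non-inferiority at a true ratio of 1.0 with n = 129 is 89.5% at margin 0.67 and 90.2% at margin 2/3. This should be fixed, but it does not call the design into question. The Table 5 point affects only whether a reader can check a borderline result.

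**What to change.** In SAP 7.2.1 and 7.2.2, state that non-inferiority is shown if the lower bound of the two-sided 95% CI for GMR312/307 is > 0.67, and superiority, tested after non-inferiority, if that lower bound is > 1.0. Make the same change to the superiority sentence in SAP 7.1. As a minor addition, set GMR312/307 and its CI to at least two decimals in Table 5 and state that verdicts use unrounded values. If outputs already exist, confirm which rule was programmed.

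The cost is a few words in three sentences and one table-shell setting. Design, data collection and sample size do not change.

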## 5 Population

### 5.1 Recruitment

Qualified participants from Study 307 who received 2 or 3 doses of an mRNA vaccine prior to Study 307 then one dose of ancestral strain NVX-CoV2373 during Study 307 will be screened in order to enroll up to 300 participants. These participants may be enrolled in 2 groups of 100 to 150 participants each, the first to receive the ancestral strain vaccine and the second, if enrolled, to receive an alternate vaccine based on a more recent variant of the SARS-CoV-2 virus. Participants will be enrolled to the 2 groups in a non-randomized fashion; the alternative treatment group, if initiated, will be conducted in staggered fashion after enrollment in the ancestral strain group has begun.

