For the secondary endpoints of cross-reaction of neutralizing and IgG antibodies induced by the ancestral strain Novavax vaccine to more recent SARS-CoV-2 variants for which appropriate assays are available, post-booster neutralizing GMTs, IgG GMEU, and GMFR for the group receiving updated NVX-CoV2373 based on recent variant(s) will be obtained using the methods noted above. Ratio of Nab GMT, difference of SCRs in Nab titers, ratio of IgG GMEUs, and differences in SCRs in IgG GMEUs for the group receiving the updated NVX-CoV2373 vaccine based on recent variant(s) is to be calculated among the same participants from Study 307.

For the secondary endpoints of antibody responses in a human angiotensin-converting enzyme 2 (hACE2) receptor binding inhibition assay to the SARS-CoV-2 ancestral strain spike protein, the same statistical methods applied for the analysis of Nabs will be applied to hACE2,b including GMT, ratio of GMT, SCR, and difference in SCRs for the group receiving ancestral strain Novavax vaccine.

For the exploratory objective of utilizing additional assays (current or to be developed) to best characterize the immune response for future vaccine development needs, including testing against emerging variants of SARS-CoV-2, the same statistical methods applied for Nab, IgG or hACE2 may be applied to evaluate immune responses based on the assays used.

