Section 7.2.2	Clarify SCR definition for ELISA (IgG) ELISA Units per CBER comments: SCR is defined as proportion of participants who achieve seroconversion \geq 4-fold increase from baseline in IgG GMEUs at Day 29 if the baseline value is equal to or above LLOQ or at least 4-fold fold rise from LLOQ if the baseline value is lower than LLOQ
Section 7.2.3	Clarify SCR definition for hACE2 titers per CBER comments: SCR is defined as proportion of participants who achieve seroconversion \geq 4-fold increase from baseline in hACE2 titers at Day 29 if the baseline value is equal to or above LLOQ or at least 4-fold fold rise from LLOQ if the baseline value is lower than LLOQ
Section 7.3.1	Clarify the grading of solicited AEs, especially Grade 4 for redness and swelling
Section 7.3.2	Delete the period of Days 29 – 181
Table 11	Add the missing 3 rd to 6 th footnotes
References	Add one missing reference (FDA 2007) for Table 10 and three missing references (Ferreira 2018, Adler 2015, and Gargano 2021) for Table 11.

SAP Version 4.0, 22 August 2023 (revised from Version 3.0, 22 May 2023)

The following is a summary of the changes made to this SAP.

Location of Change	Change/Modification in Version 4.0
Section 1.2, 7.1, 7.2 and 11	Change the terminology from GMFR _{312/307} to GMR _{312/307}
Section 7.2.1	Add the statements of the conversion from the values of Pseudovirus-based Nab response (Wuhan) in ID50 tested by Monogram for Study 2019nCoV-307 and those tested by NVX CI for Study 2019nCoV-312 to the values in the standard unit of IU/mL. Clarify the summary of Pseudovirus-based Nab response per Wuhan and Omicron BA.5 strain since Pseudovirus-based Nab response per Omicron BA.5 was not tested in Study 2019nCoV-307.
Section 7.2.2	Clarify the summary of IgG per Wuhan and Omicron BA.5 strain
Section 7.2.3	Clarify the summary of hACE2 per Wuhan and Omicron BA.5 strain due to no data of hACE2 per Omicron BA.5 strain from Study 2019nCoV-307.
Section 12 Reference	Add one Monogram report as the reference of the conversion factor (0.1458) Add one NVX CI PNA validation report as the reference of the conversion factor (0.214).

TABLE OF CONTENTS

APPROVAL SIGNATURE PAGE.....	2
SAP CHANGE HISTORY	4
TABLE OF CONTENTS.....	6
LIST OF TABLES.....	8
LIST OF FIGURES	8
LIST OF ABBREVIATIONS	9
1 INTRODUCTION.....	11
1.1 Study Design	12
1.2 Sample Size Rationale	13
1.3 Scope of the Analysis Plan	13
2 OBJECTIVES AND ENDPOINTS	14
3 ANALYSIS SUBSETS	16

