- Two-sided 95% CIs of the difference in SCRs in IgG GMEU **28 days after a second (or subsequent) booster dose** of NVX-CoV2373 in Study **2019nCoV-312** relative to time of Day 1 dose in Study **2019nCoV-307** versus **28 days after a first booster dose** of NVX-CoV2373 in Study **2019nCoV-307** relative to time of Day 1 dose in Study **2019nCoV-307** among the same participants will be based on the method of confidence interval for the difference in two correlated proportions by Tango (SAP Section [11.6](#)). Non-inferiority will be demonstrated if the LB of the 95% exact CIs for the difference of SCRs (SCR₃₁₂ – SCR₃₀₇) in IgG GMEUs is higher than –10%.

As the 3rd secondary objectives of characterizing the cross-reaction of neutralizing and IgG antibodies induced by the ancestral strain Novavax vaccine to more recent SARS-CoV-2 variants and any other variants for which appropriate assays are available, the derived/calculated endpoints of IgG response for **the group receiving updated Novavax COVID-19 Vaccine based on recent variant(s)** will include IgG GMEU at Day 1 and Day 29, GMFR_{Post/Pre} (Day 29 vs. Day 1), GMR_{312/307}, SCRs (Day 29 vs. Day 1), and difference in SCRs (SCR₃₁₂ – SCR₃₀₇) in

IgG GMEU to be calculated using the same calculations and comparison periods as noted above for the group receiving ancestral strain Novavax vaccine.

Please note above parameters of IgG data (Wuhan) from both studies of Study 2019nCoV-307 and 2019nCoV-312 will be presented together and above parameters of IgG data (Omicron BA.5) from both studies will be presented together to evaluate the secondary endpoints.

7.2.3 hACE2 Receptor-binding Inhibition Titers for SARS-CoV-2

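### The secondary objective on cross-reaction induced by the ancestral vaccine is assigned to the updated-vaccine group, and its endpoint still promises a BA.5 Nab comparison that Study 307 cannot supply

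*SAP*

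**What the plan says.** The third secondary objective (Protocol Section 3, Table 2; SAP Section 2, Table 3) concerns the "cross-reaction of neutralizing and IgG antibodies induced by the ancestral strain Novavax vaccine to more recent SARS-CoV-2 variants". Its endpoint reads: "Post-booster neutralizing GMTs and IgG GMEUs compared with post-first booster results from Study 307".

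The analysis text then names a group. For Nab, SAP 7.2.1 gives the derived endpoints to "the group receiving updated Novavax COVID-19 Vaccine based on recent variant(s". For IgG, SAP 7.2.2 restates the aim of "characterizing the cross-reaction of neutralizing and IgG antibodies induced by the ancestral strain Novavax vaccine to more recent SARS-CoV-2 variants" and names the same group. Protocol 9.3.2 agrees: "GMFR for the group receiving updated NVX-CoV2373 based on recent variant(s) will be obtained using the methods noted above". Protocol 5.1 describes two groups, "the second, if enrolled, to receive an alternate vaccine based on a more recent variant".

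Both SAP sections end with sentences on Omicron BA.5 that name no group. SAP 7.2.1 presents BA.5 Nab from Study 312 alone, as GMT, GMFR Post/Pre and SCR. SAP 7.2.2 presents BA.5 IgG from both studies side by side. The Version 4.0 entry in the SAP change history gives the reason for the difference: "Pseudovirus-based Nab response per Omicron BA.5 was not tested in Study 2019nCoV-307". That entry describes the current version and matches its text.

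**The concern.** Cross-reaction induced by the ancestral vaccine can be seen only in people who were boosted with it. People boosted with a variant-based product show that product's response, which may be homologous or close to it. A programmer who follows the named group would build the tables for this objective in the updated arm, and a report that carries over the objective's wording could present the updated vaccine's variant response as breadth of the ancestral vaccine.

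The ratio itself changes meaning there as well. SAP 7.2.1 defines GMR312/307 as a second or later booster of NVX-CoV2373 against a first. In the updated group it combines a change of strain with a change of booster number.

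The endpoint wording is a separate problem. It promises a Study 307 comparison for Nab as well as IgG, and the main recent variant named in the SAP has no Study 307 Nab result.

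**Working it through.** The plan states no figure for this objective: no margin, hypothesis or sample size. The check is therefore a comparison of passages.

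**Step 1: which group each objective names.**

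| Objective | Section | Group named |
|---|---|---|
| Primary, Nab GMT ratio | SAP 7.2.1 | Ancestral |
| First secondary, Nab SCR | SAP 7.2.1 | Ancestral |
| Second secondary, IgG | SAP 7.2.2 | Ancestral |
| Third secondary, Nab cross-reaction | SAP 7.2.1; Protocol 9.3.2 | Updated |
| Third secondary, IgG cross-reaction | SAP 7.2.2; Protocol 9.3.2 | Updated |

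The SAP names a group objective by objective. In the third-objective sentences it also refers to the ancestral group, as the group whose calculations are to be copied. The two groups are thus told apart within the sentence that makes the assignment, so this is a stated rule and not a missing detail.

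**Step 2: which of the five listed statistics exist for BA.5.** The list in SAP 7.2.1 and 7.2.2 is GMT (or GMEU), GMFR Post/Pre, GMR312/307, SCR, and the SCR difference.

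| Statistic | Samples needed | BA.5 Nab | BA.5 IgG |
|---|---|---|---|
| GMT or GMEU | Study 312 Day 1, Day 29 | Yes | Yes |
| GMFR Post/Pre | Study 312 Day 1, Day 29 | Yes | Yes |
| SCR, Day 29 vs Day 1 | Study 312 Day 1, Day 29 | Yes | Yes |
| GMR312/307 | Day 29 of both studies | No | Yes |
| SCR difference | Study 307 Day 1 and Day 29; Study 312 Day 29 | No | Yes |

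For BA.5 Nab, 5 − 2 = 3 statistics remain. These are the three that the closing BA.5 sentence of SAP 7.2.1 lists. The two that fail do so in either vaccine group. They remain in the general list for the objective, which names no strain, and the endpoint in Protocol Table 2 and SAP Table 3 still implies the comparison.

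**Step 3: what the text commits to in the ancestral group.** The explicit third-objective sentences commit to the updated group. The BA.5 sentences commit to BA.5 results without a group. No sentence links ancestral group, recent variant and third objective.

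**Step 4: would reassignment disturb the design?** The sample-size tables (Protocol Table 5, SAP Table 2) belong to the primary Nab endpoint in the ancestral group. With SD 0.61 on the log10 scale, two-sided 95% confidence, 90% power and true ratio 1.0, δ = log10(1.0) − log10(0.67) = 0.1739. Then n = (0.61 × (1.960 + 1.282) / 0.1739)² ≈ 129.3, or 130 rounded up, against the stated 129. A noncentral t calculation gives 132 with margin 0.67 and exactly 129 with margin 1/1.5. The table is reproduced closely, and nothing in it depends on the third secondary objective. Protocol Table 1 schedules Day 1 and Day 29 serology for every participant, so the ancestral-group samples are already planned.

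**The case against.** The best defence is that the BA.5 results will exist for the ancestral group anyway. The updated-group list is not worded as exclusive. The BA.5 IgG sentence in SAP 7.2.2 refers back to parameters defined above it, and those include the ancestral-group list. In SAP 7.2.1 the group-free Wuhan sentence serves the primary Nab endpoints, which exist only in the ancestral group, so reading the neighbouring BA.5 sentence as covering that group too is natural. This stands. It shows that ancestral-group BA.5 summaries may be produced even if the second group never opens. It does not correct an explicit assignment made in three places.

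Second, Version 4.0 of the SAP already deals with the missing comparator by limiting BA.5 Nab to Study 312, and GMR312/307 can still be computed for Wuhan Nab. This also stands. What is left is an endpoint and a general list that were not brought into line.

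Third, the objective is limited to variants with a suitable assay. That can excuse an absent Study 307 comparator, but it has no bearing on which vaccine group is analysed.

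Fourth, the updated group looks likely to be enrolled: SAP 3.2 describes it as following the ancestral group, and SAP Section 9 gives it its own Day 29 analysis. That weakens any worry about an empty analysis. It leaves the mismatch of product untouched.

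**Conclusion.** The analysis group for the third secondary objective is misassigned for both Nab and IgG in SAP 7.2.1, SAP 7.2.2 and Protocol 9.3.2. The stated endpoint promises a Study 307 Nab comparison that cannot be made for BA.5. It should be corrected. The reach is one secondary objective without a margin; the primary endpoint is not touched.

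A reader might infer that the plan cannot answer the objective at all, that every listed statistic will be computed only in the wrong arm, or that nothing will be reported if the second group is not opened. The documents do not support these readings. The BA.5 sentences are not confined to the updated group, BA.5 IgG is planned from both studies, and the BA.5 Nab presentation already leaves out the Study 307 contrast.

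The conclusion assumes that BA.5 is the recent variant of interest, since it is the one the SAP's immunogenicity sections name. Study 307 is said to have examined Omicron strains, but subvariants and assays are not given, so comparators for other variants cannot be judged. The table shells are not in the documents and may already split results by group.

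**What to change.** In SAP 7.2.1, SAP 7.2.2 and Protocol 9.3.2, name the group receiving ancestral NVX-CoV2373 as the analysis group for the third secondary objective. Move the same statistics for the updated group under a separate heading.

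State that BA.5 IgG in the ancestral group is compared with Study 307 within participant. For BA.5 Nab, list only GMT, GMFR Post/Pre and SCR from Study 312, and say that no GMR312/307 or SCR difference is calculated. Amend the endpoint in Protocol Table 2 and SAP Table 3, and the list of statistics for this objective, to match.

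The cost is protocol and SAP wording plus existing table shells run on the ancestral group. No extra samples are needed, and no stated sample size, margin or power changes.
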